Samples for microbiome analysis were collected at baseline (Visit 1), Day 14 (Visit 2), and Day 90 (Visit 4). Before collecting samples, each patient was asked to rinse with plain water prior and rest for 5 minutes. Sample collection was performed by gently wiping the buccal and tongue mucosa separately 10 times with three different cotton swabs. Samples were allowed to air dry at room temperature and individually placed in labeled containers with the patient's unique sequential subject identification number and day of collection. These samples were stored in a secure location at -20°C until utilized for microbiome analyses.

[4] Study Design Table

Protocol Study Design and Schedule of Assessments

Evaluation	Screening (0-2wks to Baseline)	Baseline (Visit 1) Day 0	Visit 2 Day 14 (± 3 d)	Visit 3 Day 45 (± 7 d)	Visit 4 Day 90 (± 7 d)
Informed Consent	x				
Inclusion / Exclusion	x	x			
Demographics	x				
Pregnancy Test		x			x
Medical History / Update	x	x	x		x
Medications / Update	x	x	x		x
Periodontal History	x		x		x
Oral Examination	x	x	x		x
Collect Specimen w Swab		x	x		x
Modified Gingival Index / MGI		x	x		x
Bleeding On Probing / BOP	x				x
Probing depth	x	x			x
Turesky modification Plaque Index		x	x		x
Scaling	x				
Eligibility	x				
X-rays		x			x
Enrollment / Randomization		x			
Dispense oral hygiene kit / Diary		x			
Schedule next appt	x	x	x		
Collect residual oral hygiene kit with Diary and distribute oral hygiene kit with Diary for next phase			x	x	
Collect residual oral hygiene kit / Diary					x

[5] Protocol Synopsis

1. Study Title: The Efficacy and Safety of stabilized chlorine dioxide mouth rinse in Therapy of Peri-implant mucositis
2. Study Design: Single Center, randomized, double blind masking, parallel, two-arm clinical study.
3. Objective: The purpose of this study was to analyze efficacy of stabilized chlorine dioxide as a chemical adjuvant for treatment of peri-implant mucositis in a non-surgical treatment protocol with a 3-month follow-up.
4. Study Treatments: 1) Stabilized chlorine dioxide (associated with periodontal basic therapy); and 2) control (placebo associated with periodontal basic therapy).
5. Number of Patients: A total of 54 patients in one clinical site at Stony Brook were randomized, 27 patients received 1) Stabilized chlorine dioxide (associated with periodontal basic therapy); and 27 patients received 2) control (placebo associated with periodontal basic therapy).

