6. Study Duration and Visits: The study duration was (3 months) and was comprised of a total of 4 visits: Screening and hygienic phase therapy (weeks -2 to -1), Baseline (Visit 1, Day 0), Visit 2 (14 days), Visit 3 (45 days), Visit 4 (90 days).
7. Subjects received an Oral Hygiene Kit at Visit 1. The Modified Gingival Index (MGI), Bleeding on Probing (BOP) and Plaque Index (PI), Pocket depth and radiographs were measured, and all oral tissues examined (baseline examination). Subjects returned for Visit 2 in 14 days \pm 3 days to: 1) assess and record changes in indices and oral health and any adverse conditions. Visit 3 (45 days \pm 7) was a compliance visit for study drug utilization. Visit 4 (90 days \pm 7) was a repeat of Visit 1. Samples for microbiome analysis were collected at baseline (Visit 1), Day 14 (Visit 2), and Day 90 (Visit 4).
8. All parameters for clinical exam were calibrated between the examiners involved with the study.

[6] Study Materials (Oral Hygiene Kit)

STUDY DRUG

Both the active and placebo drugs were provided in liquid form, intended for oral administration. Sample products were labeled by the manufacturer and shipped directly to the site.

ADMINISTRATION

After tooth brushing in the morning and evening, the study product was administered orally using a cup that measures 15 mL of oral rinse, swishing in the oral cavity for 30 seconds and expectorating.

[7] Subjects

Subject recruitment occurred at the discretion of the Principal Investigator. After being recruited, potential subjects were informed of the purpose of the study and guided through HIPAA documentation and the informed consent process. Upon their understanding of the study, HIPAA regulations, and their agreement with the terms of the informed consent, subjects indicated so by signing the forms. The eligibility of potential subjects was determined through a series of screening interviews and an oral examination. Following screening, those potential subjects who retained eligibility were enrolled in the study at the discretion of the Principal Investigator. Approximately 75 subjects were screened to provide 54 enrollees. Once these subjects were randomized, study enrollment was complete.

Number of subjects: 54 subjects

Age: 18 years to 80 years

Gender: Both male and female subjects entered this study.

Remaining Natural Teeth: Minimum of 20

[8] Subject Eligibility Criteria

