The patients' data on the three measures were recorded within the Excel Workbooks under three tabs representing the first, second, and third clinical observation periods. So each tab recorded three measures. The first and last tabs recorded probing depth, gingival index, and plaque. The second visit included only gingival index and plaque. Each patient had an individual Excel Workbook. Data were sorted into analysis format through two Excel macros that created a single master data for global scores and a single one for implant and non-implant scores. Data files were saved in comma separated value (csv) format in both wide and long formats for R and SPSS data management, inspection, cleaning, and analyses.

Since many individual variable distributions varied substantially from normal, a gamma log-link function was applied to reduce bias in most statistical tests.

Label Key and Lot #s for Peri-Implant Mucositis Study with Stony Brook University

Rowpar Pharmaceuticals, Inc., released the test material label codes after completion of the clinical study and statistical analysis of the data. The products were labelled as follows:

Study Number: SBU-RPR-Peri-Implant Mucositis-2018

Oral Rinse A: ClōSYS Placebo Oral Rinse, Lot #: 2-80516

Oral Rinse X: ClōSYS® Ultra Sensitive (Unflavored) Oral Rinse, Lot #: 8122A 14-80430

Results

Patients

Fifty-two percent (29/56) of patients in both groups had only one implant. Patients in the control group (Group A) had a total of 47 implants: 11 patients had just one implant, 13 had 2, 2 had 3, and 1 had 4 implants. In the test group (Group X), there were 42 total implants in 26 patients: 18 had 1 implant, 9 had 2, and 2 had 3 implants (see Figure 1). Table 1 gives average values (and standard error of the mean) of Gingivitis Index, Plaque score, and Probing depth at baseline.

Figure 1. Bar chart of numbers of implants per person in control group (Group A) and test group (Group X).

[figure not shown]

Table 1. Patient dental measures at baseline.

		n of patients	n of implants	Modified Gingivitis Index (MGI) (sem)	Plaque score (PS) (sem)	Probing Depth mean (sem)
Control Group (Group A)	implants	27	47	2.06 (0.048)	2.77 (0.115)	3.40 (0.109)

	non-implanted teeth			1.87 (0.039)	2.32 (0.101)	2.72 (0.099)
Test Group (Group X)	implants	26	39	2.82 (0.049)	2.84 (0.057)	2.447 (0.080)
	non-implanted teeth			2.01 (0.028)	2.99 (0.078)	2.65 (0.079)

Global Score Analyses

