Slope of probing depth, time 1 to 3	57	-1.47	0.015	-0.10632	0.323886
Slope of gingivitis index, time 1 to 3	57	-0.99	-0.03	-0.24351	0.221807
Slope of plaque score, time 1 to 3	57	-1.53	-0.045	-0.45254	0.358255
Valid N (listwise)	57				

Global Probing Depths (GPD)

Global probing depth (GPD) collected at the first visit did not differ significantly between groups; control group's (Group A) initial GPD was 2.76 (SEM = 0.092) interval, and 2.68 (0.071) for test group (Group X), a non-significant statistical difference ($p = 0.48$).

Neither did the GPD score differ between final visits of control group (Group A) (GPD = 2.64 (0.130) and test group (Group X) (GPDI = 2.37, (0.166), $t = 1.27$, $df = 55$, $p = 0.28$. Nonetheless, the GPD decreased significantly for control group (Group A), ($p = 0.028$; for X, $p < 0.001$) for both groups, but the group decreases were not significantly different from each other. Both mouthwashes reduced probing depth similarly.

The key signal of treatment effectiveness is a statistically significant treatment-by-time interaction, where improvement over time is greater for one treatment than another. Nearly parallel lines in Figure 2 and statistical testing indicated no appreciable and significant treatment-by-time interaction for GPD (See Figure 2, Figure 3).

Figure 2. Interaction plot showing that group assignment did not interact with time for probing depth.

[figure not shown]

Figure 3. Boxplots of probing depth results from treatment by control group (Group A) and test group (Group X). Probing depth was not affected differentially by the mouthwash treatments. Both conditions reduced probing depth slightly but not statistically significant.

Global Plaque Score

Control group (Group A) and test group (Group X) differed significantly in global plaque score (GPS) at initial assessment, requiring an additional analysis of covariance to confirm that a significant time by treatment interaction was not an artifact from the initial difference in GPS (See interaction plot, Figure 4, detailed in Figure 5). The test group's (Group X) initial average GPS was 3.00 (SEM = 0.071) versus 2.35 (0.097) for the control group (Group A), a significant difference ($t = -5.45$, $df = 50$, $p < 0.001$). At assessment 3, the last observation, the test group's (Group X) GPS (1.57, SEM = 0.110) was significantly lower than that for the control group (Group A); GPS = 1.98 (0.110), $t = 2.633$, $df = 55$, $p = 0.011$.

[figure not shown]

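### The analysed numbers (53, 56 and 57) cannot be reconciled with the 54 patients (27 + 27) reported as randomised

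*Combined protocol and SAP*

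**What the plan says.** Section [5] Protocol Synopsis, item 5, states: "A total of 54 patients in one clinical site at Stony Brook were randomized, 27 patients received 1) Stabilized chlorine dioxide", and gives the other 27 placebo. Section [7] Subjects adds: "Approximately 75 subjects were screened to provide 54 enrollees. Once these subjects were randomized, study enrollment was complete".

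The Results, under Patients, give a different total: "Fifty-two percent (29/56) of patients in both groups had only one implant". For the control arm they report "11 patients had just one implant, 13 had 2, 2 had 3, and 1 had 4 implants", 47 implants in all. For the test arm they say "there were 42 total implants in 26 patients: 18 had 1 implant, 9 had 2, and 2 had 3 implants".

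Table 1 lists 27 control patients with 47 implants and 26 test patients with 39 implants. Table 3 prints N = 57 in every row, including the listwise count, and Table 2 has error df 55. Error df is 204 in Table 4 and 102 in each of Tables 5, 6 and 7.

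Section [8] lists reasons for withdrawal. No section says how many patients withdrew, gives disposition by arm, defines an analysis set, or explains why N is 53, 56 or 57.

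**The concern.** A randomised comparison is protected from selection only if the patients analysed are those randomised, in the arms to which they were allocated. Dropout lowers the analysed number. Nothing in the described conduct can raise it above the number randomised, because enrolment is said to have closed at 54.

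The test arm appears as 27 allocated, 29 in the implant breakdown and 26 in Table 1, while the control arm is 27 in all three places. Every F statistic and p-value behind the Conclusions depends on these counts and error df. Until they are traced to the allocation list, a reader cannot tell whether the comparison is still the randomised one.

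**Working it through.** **1. Implant breakdown (Results, Patients).**
- Control: 11 + 13 + 2 + 1 = 27 patients; 11×1 + 13×2 + 2×3 + 1×4 = 47 implants. Both agree with Table 1.
- Test: 18 + 9 + 2 = 29 patients; 18×1 + 9×2 + 2×3 = 42 implants. The implant total agrees with the sentence; the stated 26 patients do not.
- Overall: 27 + 29 = 56. One-implant patients: 11 + 18 = 29, and 29/56 = 51.8%, the printed 52%. So 29 test patients were used in the calculation.

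**2. Is the 57 in Tables 2 and 3 a typing slip?** N can be recovered in two ways from the slope rows (SD and mean from Table 3, sums of squares from Table 2).

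| Slope | Corrected SS / SD² + 1 | (Total SS − corrected SS) / mean² |
|---|---|---|
| Probing depth | 5.875 / 0.323886² + 1 = 57.00 | 0.644 / 0.10632² = 56.97 |
| Gingival index | 2.755 / 0.221807² + 1 = 57.00 | 3.380 / 0.24351² = 57.00 |
| Plaque | 7.187 / 0.358255² + 1 = 57.00 | 11.674 / 0.45254² = 57.00 |

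The printed F values also follow with 55 error df: 0.125/(5.75/55) = 1.196, 0.485/(2.27/55) = 11.75 and 4.019/(3.169/55) = 69.75, against 1.191, 11.748 and 69.751. With 54 patients the error df would be 52 and the corrected SS 5.560, 2.608 and 6.802. The global analyses were run on 57.

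**3. Arm sizes within the 57.** The overall mean is the weighted mean of the arm means, so n(test) = 57 × (overall − control) / (test − control). Baseline plaque gives 57 × (2.67895 − 2.35) / (3.00 − 2.35) = 28.8, or 28.4 to 29.3 allowing for rounding of the arm means. Final plaque (1.98, 1.57, overall 1.77386) gives 28.0 to 29.4. The split is therefore about 29 test and 28 control, each above 27.

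**4. Can zero-coded follow-up explain the excess?** Table 3 minima are 0 at times 2 and 3. The extreme slopes −1.47, −0.99 and −1.53 equal a fall to 0, over two intervals, from 2.94, 1.98 and 3.06. Zeros are therefore present at follow-up. At baseline the minima are 2.04, 1.41 and 1.47, so all 57 have real baseline scores. Coding a missed visit as 0 cannot create a baseline record.

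**5. N behind Tables 4 to 7.** Add the fitted parameters to the error df and divide by rows per patient.
- Tables 5 to 7: (102 + 4)/2 = 53. With 54 patients the df would be 104.
- Table 4: (204 + 8)/4 = 53. With 54 patients the df would be 208.
- This matches Table 1: 27 + 26 = 53.

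**6. From 29/42 to 26/39.** Removing three one-implant test patients gives (18 − 3) + 9 + 2 = 26 patients and 15 + 18 + 6 = 39 implants, exactly the Table 1 entry.

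**The case against.** The best counter-argument is that 54 is a planned figure never updated. The protocol text reads in places like a plan put into the past tense: the periodontal therapy paragraph of section [3] keeps a future tense, and section [10] still speaks of what was being considered. This stands as a possibility. The randomised total may be the wrong number, which is why the point is one of irreconcilable counts and not of proven over-analysis.

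A second argument is that 53 is simply 54 less one test-arm dropout. That fits Table 1 and Tables 4 to 7 taken alone, but not the 29-patient breakdown in the sentence that states 26.

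A third is that zero-coded dropouts link 57 to 53. They may. At time 3 the gingival index scores sum to 57 × 1.48456 = 84.62, and their squares to 56 × 0.451688² + 57 × 1.48456² = 137.05. The non-zero records must number at least 84.62²/137.05 = 52.2, so at most four are zero, and 57 − 4 = 53. This is inference, and it leaves the step from 54 to 57 unexplained.

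Four stronger readings are tempting and not supported:
- **Every result contains surplus patients.** Tables 4 to 7 fit 53, below 54. They are untraced, not over-counted.
- **Each outcome has its own set.** Tables 2 and 3 use 57 for all three outcomes, and Tables 5 to 7 share 53. The tables differ by analysis level.
- **The gingival index ANCOVA df of 51 shows a further set of 54.** That needs a three-parameter pooled model, which is not stated. The nearby df of 50 for baseline plaque shows the risk: its SEMs (0.071 and 0.097) with 29 + 28 patients give a Welch df of 49.9, so an odd df can come from the same 57.
- **The change in the gingival index effect can be quantified.** It would need the number of zero records and their arms, which are not given, and it would measure the step from 57 to 53, not the surplus over 54.

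**Conclusion.** The point holds as a failure of reconciliation. Against 54 randomised, the implant-count text has two patients too many (2/54 = 3.7%) and the global analyses three too many (3/54 = 5.6%). Table 1 and Tables 4 to 7 have one fewer. The 57 is confirmed by the tables' own sums of squares, so it is neither a misprint nor a product of zero-coding.

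Two explanations remain: the randomised total is wrong, or the global analyses include records from outside the randomisation or duplicates. The documents do not show which. The fit of 29/42 to 26/39 suggests an unreported exclusion of three patients in the test arm only, but does not prove one.

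The 29 + 28 split assumes that the printed arm means and the Table 3 overall mean come from the same 57 records. The 53 assumes one implant row and one non-implant row per patient in Tables 5 to 7, and two measures for each in Table 4. The direction and size of any effect on the gingival index result are unknown. Because the efficacy conclusion rests on these counts, this must be resolved before it is relied on.

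**What to change.** 1. Check every patient record against the randomisation list held by the third-party statistician (section [8], Assignment), looking for duplicates and for records with no allocation. If 54 proves to be the wrong figure, correct sections [3], [5] and [7].
2. Add a disposition table by arm: randomised, received rinse, attended each visit, analysed, with reasons for each loss or exclusion.
3. Correct the 26/29 test patients, the 39/42 test implants and the 54/56/57 totals.
4. Re-run the global and implant analyses on one defined set: all randomised patients, in the arm to which they were randomised. Treat missed visits as missing, never as zero, for example with a likelihood-based repeated-measures model. State its missing-at-random assumption. Print N per arm and error df with every table.
5. Hold the efficacy statements in the Conclusions until this is done.

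The cost is a record check and a re-run on data already collected. No new patients or visits are needed.

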6. Performed a Turesky modification of the Quigley-Hein Plaque Index (PI) grading on all natural teeth and implants in the dentition.
7. Assessed bleeding on probing (BOP) on all natural teeth and implants in the dentition.
8. Verified data capture.
9. X-rays
10. Full mouth Scaling
11. Randomization and dispensation of the Oral Hygiene Kit and Oral Hygiene Diary.
12. The subjects then followed their normal oral-hygiene procedures with the addition of using the study rinse, toothbrush, and toothpaste provided to them.
13. Provided diary for recording use of product rinse or placebo.
14. Provided supplies for 14 days (day 1 to day 14 of the study). Weighed and recorded the weight of test rinse or placebo, as applicable, being provided.
15. Instructed Subject to bring remaining oral rinse or placebo bottle
16. Scheduled following appointments for Visit 2 (2 weeks after base line) and Visit 3 (3 months) and noted in their study instructions and diary. Subjects were to be seen within plus or minus 7 days.

VISIT 2 - INTERIM EXAMINATION - DAY 14

This examination took place within 14 calendar days after Baseline Examination (Visit 1) \pm 3 days. The following procedures were conducted:

1. Reviewed any change in medical and dental history
2. Rinsed mouth with water and collected samples for microbiome analysis by using a cotton swab on the inside of the cheek and tongue mucosa.
3. Evaluated extra- and intra- oral areas for any mucosal irritation or pathology.
4. Performed a Modified Gingival Index (MGI) grading on all natural teeth and implants in the dentition.
5. Performed a Turesky modification of the Quigley-Hein Plaque Index (PI) grading on all natural teeth and implants in the dentition.
6. Weighed and recorded remaining test rinse or placebo as applicable.
7. Checked record for use of test rinse or placebo in the diary.
8. Provided diary for recording use of product rinse or placebo.
9. Provided supplies for 30 days (day 15 to day 45 of the study). Weighed and recorded the weight of test rinse or placebo, as applicable, being provided.
10. Confirmed appointment date scheduled for the Compliance Visit (Visit 3). The subjects were given a reminder call 2 - 3 days prior to their scheduled appointment.

VISIT 3 – COMPLIANCE VISIT – DAY 45

This examination took place within 45 calendar days after Baseline Examination (Visit 1) \pm 7 days. The following procedures were conducted:

1. Weighed and recorded remaining test rinse or placebo as applicable.

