2. Checked record for use of test rinse or placebo in the diary.
3. Provided diary for recording use of product rinse or placebo.
4. Provided supplies for remaining 45 days (day 46 to day 90 of the study). Weighed and recorded the weight of test rinse or placebo, as applicable, being provided.
5. Confirmed appointment date scheduled for the Final Examination Visit (Visit 4). The subjects were given a reminder call 2 - 3 days prior to their scheduled appointment.

VISIT 4 - FINAL EXAMINATION – DAY 90

This examination took place within 90 days following the Baseline Examination (Visit 1) \pm 7 days. The following procedures were conducted:

1. Collected the subject's diary and unused products at check-in. All partially used products were assessed for volume remaining and recorded. Used products were retained until after a monitoring visit, and then returned to the Sponsor.
2. Performed pregnancy testing on females of childbearing age.
3. Rinsed mouth with water and collected samples for microbiome analysis by use of a cotton swab on the inside of the cheek and tongue mucosa.
4. Asked the subject to report any changes in medical or dental health since the last visit.
5. Evaluated extra- and intra- oral areas for any mucosal irritation or pathology.
6. Performed a Modified Gingival Index (MGI) grading on all natural teeth and implants in the dentition.
7. Performed a Turesky modification of the Quigley-Hein Index (PI) grading on all natural teeth and implants in the dentition.
8. Assessed bleeding on probing (BOP) and probing depth on all natural teeth and implants in the dentition.
9. X-rays
10. Weighed and recorded remaining test rinse or placebo as applicable.
11. Checked record for use of test rinse or placebo in the diary.

[10] Study Timeline

Using December 2018 as a calendar starting point, the entire month would provide 20 days for recruiting. As the screening, cleaning and baseline visit can be all on the same day we were considering that subjects could begin Study Visit 1 between January 2019 and December 2019. The final study visits was conducted in March 2020. A final report concluded by December 2020.

[11] Statistical Evaluation

The primary objective of this study was to analyze efficacy of stabilized chlorine dioxide as a chemical adjuvant for treatment of peri-implant mucositis in a non-surgical treatment protocol with a 3-month follow-up.

The primary objective was determined by an examination of the following data:

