- a) Gingival inflammation (MGI)

Secondary analyses were the comparison of data with respect to product effectiveness:

- a) Reduction in bleeding on probing (BOP) and Turesky modification of the Quigley-Hein Plaque Index (PI) grading on all natural teeth in the dentition

The primary statistical analytic framework was the repeated measures analysis of variance on three primary outcomes: probing depth, gingival index, and plaque. The primary hypothesis tested was the treatment by time interaction, i.e., did one treatment work better during the observations of these three outcomes? In other words, not just the total change, but also the rate of that change might differ between treatments. The proposed analysis was based on data that were generally normally distributed and similarly. If not, data transformations or link functions were used.

Outcomes

Raw data were collected from examinations of each tooth with regard to probing depth, gingival index, and plaque. Data were collected over three time periods, recorded into patient files, and transferred to Excel Workbooks, with one Workbook per patient. Each Workbook contained three tabs, one for each visit.

The raw data were combined as two levels of indexes for the three measures. The first outcome was a global score index of probing depth, gingival index, and plaque measurement. The global index was derived from individual tooth scores for each measure divided by the number of teeth measured. The second index derived from the same raw data described the three measures in terms of average scores for implant and non-implant teeth.

For the second analysis, implanted tooth data were separated from normal teeth data within each patient. Implant scores for each patient were averaged for probing depth, gingival index, and plaque scores. If a patient had one implant, each score was identical to the single measurement. With more than one implant, a single implant score for each patient was derived from averaging each of the three measures over the three observation periods. Likewise for each patient, the non-implanted teeth measures were averaged for each of the three times of assessment.

Individual patient data of the averages of the implant and non-implant teeth were calculated for each time period and transferred to a master data sheet.

Data Management and Statistical Analysis

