From raw data of individual teeth, each patient received a global index of periodontal disease, gingival index, and plaque for each visit. The global index for each of these measurements was found by dividing the sums of patient probing depth, gingival index, and plaque findings collected for each tooth by the number of teeth assessed. Over the three assessment periods, global scores of probing depth, gingival index, and plaque were collected for the first and last visits with probing depth scores not collected during the second visit. These outcomes are measured as individual slopes of responses across the three observation visits. The slope represents the rate of change.

The overall view of the response of each measure to the treatment group is summarized in the following general linear model Table 2. Table 3 shows the cell statistics for the slopes of each condition and outcomes reported in Table 2.

Table 2. Master table of variance components attributable to treatment on individual rates of change on the three measures: probing depth, gingival index, and plaque.

Source	Variable	Type III SS	df	MS	F	Sig.
Group	Slope of probing depth, time 1 to 3	0.125	1	0.125	1.191	0.28
	Slope of gingivitis index, time 1 to 3	0.485	1	0.485	11.748	0.001
	Slope of plaque score, time 1 to 3	4.019	1	4.019	69.751	0.000
Error	Slope of probing depth, time 1 to 3	5.75	55	0.105		
	Slope of gingivitis index, time 1 to 3	2.27	55	0.041		
	Slope of plaque score, time 1 to 3	3.169	55	0.058		
Total	Slope of probing depth, time 1 to 3	6.519	57			

Slope of gingivitis index, time 1 to 3	6.135	57
Slope of plaque score, time 1 to 3	18.861	57
Corrected Total	Slope of probing depth, time 1 to 3	5.875
	Slope of gingivitis index, time 1 to 3	2.755
	Slope of plaque score, time 1 to 3	7.187
	R Squared = .021 (Adjusted R Squared = .003)	
	R Squared = .176 (Adjusted R Squared = .161)	
	R Squared = .559 (Adjusted R Squared = .551)	

Table 3. Details of cell statistics for analysis described in Table 2.

Descriptive Statistics					
	N	Minimum	Maximum	Mean	Std. Deviation
Probing depth at time 1	57	2.04	4.63	2.71614	0.432843
Probing depth at time 3	57	0	4.42	2.50351	0.804056
Gingivitis index at time 1	57	1.41	2.23	1.97158	0.172065
Gingivitis index at time 2	57	0	2	1.71754	0.364095
Gingivitis index at time 3	57	0	1.92	1.48456	0.451688
Plaque score at time 1	57	1.47	3.54	2.67895	0.555475
Plaque score at time 2	57	0	3.11	2.19614	0.596444
Plaque score at time 3	57	0	2.92	1.77386	0.618124

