There is a clear advantage to using ClōSYS® Ultra Sensitive oral rinse treatment (test rinse X) in terms of plaque and gingival index. In addition, ClōSYS® Ultra Sensitive oral rinse (test rinse X) appeared to have a preferential benefit for implant sites, over both control treatment (placebo rinse A) and over non-implant sites. The ClōSYS® Ultra Sensitive rinse (test rinse X) significantly reduced the plaque index and gingival index as compared to initial measures and those in control group (placebo rinse A) ($p < 0.001$). The observation of higher initial gingivitis scores for the ClōSYS® Ultra Sensitive oral rinse (test rinse X) did not affect the superiority of this test group treatment. In controlling for the inequality at baseline, and analysis of covariance showed the reduction of the plaque score remained significantly better in the ClōSYS® Ultra Sensitive oral rinse group (test rinse X) than for the control group (placebo rinse A) ($p < 0.001$). Also, using pre-post difference scores and slopes of the scores over time showed the treatment effect to be robust to the mismatch of initial levels of gingivitis and plaque ($P < 0.001$ for both).

Both groups improved from the use of mouthwashes, but the ClōSYS® Ultra Sensitive oral rinse (test rinse X) improved more and at a faster rate ($p < 0.001$) compared to the control group (placebo rinse A). There was no apparent effect on periodontitis between the two intervals in which it was measured.

Implant sites were significantly more ($p < 0.001$) and faster ($p < 0.001$) improved in the ClōSYS® Ultra Sensitive oral rinse group (test rinse X) than the other non-implanted teeth and in the control group (placebo rinse A).

Both ClōSYS® Ultra Sensitive oral rinse (test rinse X) and placebo rinse (rinse A) tested are safe to oral tissues and did not show any adverse effects.

Both ClōSYS® Ultra Sensitive oral rinse (test rinse X) and placebo rinse (rinse A) tested are safe to oral tissues and do not have any adverse effects.

Signature Page

[name]

Principal Investigator

[name] [name], PhD

REFERENCES

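### The global slopes are the baseline-to-Day-90 change divided by two, so they support a larger 90-day change but give no separate evidence that the test rinse worked faster

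*Combined protocol and SAP*

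**What the plan says.** Section [11], Statistical Evaluation, makes the treatment-by-time interaction the primary hypothesis and separates two questions: "not just the total change, but also the rate of that change might differ between treatments".

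The Global Score Analyses then define the outcome: "These outcomes are measured as individual slopes of responses across the three observation visits", followed by "The slope represents the rate of change". The time scale used for the slope is not stated. Table 2 tests group on these slopes and Table 3 gives their means.

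The Protocol Synopsis, item 6, sets the post-baseline visits at "Visit 2 (14 days), Visit 3 (45 days), Visit 4 (90 days"). Visit 3 is a compliance visit, so the three clinical time points are Days 0, 14 and 90. Data Management and Statistical Analysis adds: "The second visit included only gingival index and plaque". Probing depth thus has two time points.

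The Conclusions say that the test rinse group "improved more and at a faster rate", with p < 0.001. For implant sites they attach one p-value to the amount of improvement and another to its speed. They also cite pre-post differences and slopes together as showing that the effect withstands the baseline imbalance. Similar wording on speed appears under Global Gingival Index Score (Figure 7 legend) and in the implant subsections.

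**The concern.** The time points are 14 and 76 days apart. Day 14 is the only clinical measurement between baseline and the end, so it alone could separate how quickly the arms diverged from how far. A slope that ignores it cannot answer the rate question posed in section [11]. Two rinses with the same Day 90 change would get the same slope, even if one acted within two weeks and the other acted late.

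Two things are at stake. An efficacy conclusion about speed appears beside the conclusion about size with no separate test behind it. And one comparison is counted twice when difference scores and slopes are offered together as robustness evidence.

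**Working it through.** **Inputs.** Table 3, N = 57, pooled over arms, means as printed (times 2 and 3 include minimum values of 0):

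| Outcome | Time 1 | Time 2 | Time 3 | Printed mean slope |
|---|---|---|---|---|
| Gingival index | 1.97158 | 1.71754 | 1.48456 | -0.24351 |
| Plaque | 2.67895 | 2.19614 | 1.77386 | -0.45254 |
| Probing depth | 2.71614 | none | 2.50351 | -0.10632 |

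**1. Reproduce the printed slopes.** A least-squares slope on codes 1, 2, 3 has weights -0.5, 0, +0.5, so it equals (time 3 - time 1)/2.
- Gingival index: (1.48456 - 1.97158)/2 = -0.24351.
- Plaque: (1.77386 - 2.67895)/2 = -0.452545.
- Probing depth: (2.50351 - 2.71614)/2 = -0.106315.

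All three match to rounding.

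**2. Try the day scale.** On days 0, 14, 90 the weights are -0.00739, -0.00441 and +0.01180 per day. Gingival index gives -0.00463 per day, or -0.208 per 45 days. Plaque gives -0.00855 per day, or -0.385 per 45 days. Neither matches.

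**3. Solve for the Day 14 weight.** Suppose one set of weights summing to zero produced both slopes, with b on time 2 and c on time 3:
- Gingival index: -0.25404b - 0.48702c = -0.24351.
- Plaque: -0.48281b - 0.90509c = -0.45254.

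The solution is b = -0.0005 and c = 0.5002. Rounding of the printed figures allows b from about -0.003 to 0.002. The Day 14 weight is zero within that precision.

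**4. Tie Table 3 to the test in Table 2.** 56 × SD² of the slopes gives 5.875 (probing depth), 2.755 (gingival index) and 7.187 (plaque), the corrected totals in Table 2. The tested variables are these slopes.

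**5. Show that the rate test is the change test.** For plaque, √69.751 = 8.352. Global Plaque Score reports t = 8.35 as a single result for both the size and the rate of change. The arm difference in slope implied by Table 2 is √[SS × (n1 + n2)/(n1 × n2)]. With SS = 4.019 and arms assumed to be 27/30 or 28/29 (the split of the 57 is not printed), this is 0.53, or 1.06 once doubled. The text gives changes of -1.43 and 0.365. Reading the second as a fall, since 2.35 - 1.98 = 0.37, the difference is 1.43 - 0.365 = 1.065.

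**6. Describe the pooled time course.**
- Gingival index fell 0.25404 by Day 14 (0.01815 per day) and 0.23298 over the next 76 days (0.00307 per day), a ratio of 5.9. Share by Day 14: 0.25404/0.48702 = 52%.
- Plaque fell 0.48281 (0.03449 per day) and then 0.42228 (0.00556 per day), a ratio of 6.2. Share by Day 14: 0.48281/0.90509 = 53%.

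A straight line in visit number would put 50% of the fall at the second visit, so the means are almost linear in visit number and clearly not linear in days.

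**The case against.** A reader might infer that the speed claim has no evidence behind it at all. The documents do not support that. Both arms had the same nominal 90-day follow-up, so a larger total fall is a larger average rate over 90 days. The group F is unchanged by halving, so Table 2 supports an average-rate statement as well as a total-change statement. Suppose a share f of the Day 90 arm difference in change was present at Day 14. As f runs from 0 to 1, the arm difference in a day-scaled slope, per 90 days, runs from 1.13 to 0.71 for plaque (total 1.065) and from 0.39 to 0.25 for gingival index (total 0.369, from Table 2 as in step 5). The sign reverses only if f exceeds 0.01180/0.00441, about 2.68.

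A reader might also take the six-fold per-day ratios as proof that visit coding distorts the comparison. They do not show that. Visit coding describes the pooled means well, and figures pooled over arms cannot show bias between arms.

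Other analyses also bear on time: a repeated measures analysis of the global gingival index (F = 8.141, p = 0.0046) and a time-by-group term in Table 5, whose measure is labelled GGI (F = 35.047). They are separate from the slope test, but each has 1 degree of freedom and none isolates early change. The F of 79.0 cited under Implants and Gingival Index for more and faster improvement is the implant-by-group term of Table 6, a between-subjects table with no time term.

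Figures 4, 6 and 7 may show Day 14 by arm. They are missing from the copy reviewed, and nothing here rests on their absence. The text and tables print no global Day 14 mean or contrast by arm.

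Finally, Global Plaque Score openly gives one t for both descriptions, and no speed advantage is claimed for probing depth. Both points stand, and they limit the problem mainly to the gingival and plaque wording.

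**Conclusion.** Wrong as written; it should be fixed. The global slope analysis is the baseline-to-Day-90 comparison on a halved scale. It supports a larger average change over 90 days and carries no information on speed or timing separate from that change. Reporting faster as a result alongside more is unsupported by it, and slopes and difference scores are one piece of evidence. The baseline-adjusted ANCOVAs are a separate analysis and are not affected by this point.

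The direction and significance of the total-change result are not shown to alter. Whether the test rinse acted earlier is open: the text and tables give no arm-level Day 14 figures from which to compute it.

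The conclusion rests on the coding inferred from the arithmetic, since the documents do not state it, and on the printed Table 3 means. It is established for the global scores only. The implant-site plaque slopes (-0.151 and -0.463) could not be checked in the same way.

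**What to change.** 1. Analyse gingival index and plaque with visit as a three-level factor. Do not substitute a linear term in study day: the six-fold change in the pooled per-day rate contradicts a straight line in days.
2. Report the baseline-adjusted arm difference at Day 14 and at Day 90, each with a confidence interval.
3. Define faster by the Day 14 contrast. Unless that contrast supports it, remove faster as a separate result from Global Gingival Index Score, the implant subsections with their figure legends, and the Conclusions.
4. State how time was coded in the slopes, including those for implant sites, and describe the global slope as half the 90-day change.
5. Stop presenting slopes and pre-post differences as independent confirmations, and do not describe a probing-depth rate as distinct from its change.

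The cost is a re-analysis of data already collected and edits to the text. The possible loss is the speed claim; the total-change results stay as they are.
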